10.4 DEFINITION OF SEVERITY OF ADVERSE EVENTS

Adverse events must be graded for severity. A severity category of mild, moderate, severe or life threatening as defined below, must be entered on the AE CRF page.

- 1. MILD Awareness of signs or symptoms, but they are easily tolerated and no disruption of normal daily activity.
- 2. MODERATE Enough discomfort to cause interference with normal daily activity. No treatment or medical intervention is indicated.
- 3. SEVERE Inability to work or perform normal daily activity; medical intervention is indicated.
- 4. LIFE THREATENING/DISABLING An immediate threat to life or leading to a permanent mental or physical conditions that prevents work or performing normal daily activities. Treatment or medical intervention is required in order to maintain survival.

10.5 REPORTING OF ADVERSE EVENTS

Any Serious adverse event (SAE) and device respectively procedure-related (Relatedness: definite, probably and possibly) Adverse Effect (SADE), must be fully recorded utilizing the sponsor provided SAE form and reported in writing by the Principal Investigator to Envivo Bio Inc. within 24 hours of becoming aware of the event.

The PI will complete the Serious Adverse Event Form and email a scanned copy to Envivo Bio Inc. sponsor and the medical monitor contacts as follows:

Additional information (follow-up) about any SAE or SADE unavailable at the initial reporting should be forwarded by the site to the Envivo Bio Inc. as soon as they become available (such as hospital discharge).

Envivo Bio Inc. will review and assess with the PI any SAE's and any serious device/procedurerelated adverse effects. Envivo Bio Inc. ensures that reporting requirements according to the local regulations are fulfilled.

All SAE's which are considered as device- or procedure-related will be reported to IRB by the PI.

Subjects who have had an SAE during the Treatment Phase must be followed clinically until all parameters (including laboratory) have returned to normal, have stabilized, or are otherwise explained. The study period for the purpose of SAE reporting is defined as the period from time of informed consent until 14 days after the End of Study.

If the investigator detects a SAE in a trial subject after the end of the period of observation, and considers the event possibly related to the prior trial, he should contact the sponsor to determine how the AE should be documented and reported.

10.6 DOCUMENTATION OF AEs

All AEs reported by the subject or detected by the investigator will be documented on the appropriate pages of the case report form (CRF). AEs must also be fully documented in the subject's source documents.

If the adverse event is serious, the investigator must complete, in addition to the "Adverse Event" page, a "Serious Adverse Event" Report Form at the time the serious adverse event is detected.

Every attempt should be made to describe the adverse event in terms of a diagnosis. If a clear diagnosis has been made, individual signs and symptoms will not be recorded unless they represent atypical or extreme manifestations of the diagnosis, in which case they should be reported as separate events. If a clear diagnosis cannot be established, each sign and symptom must be recorded individually.

10.7 PREGNANCY

Female subjects should immediately inform the Investigator of any pregnancies during the study. The site should report all pregancies within 48 hours to the Envivo Bio Inc. Project Manager using the SAE form.

11. STATISTICAL ANALYSIS PLAN

Due to the small sample size and the study objectives, the statistics will be mainly descriptive by nature. For categorical variables, summary tables will be provided giving sample size, absolute

and relative frequency. For continuous variables summary tables will be provided giving sample size, arithmetic mean, standard deviation, standard error of the mean (SEM), median, minimum and maximum, percentiles and 95% CI (Confidence Interval) for means of variables.

Tables of descriptive statistics will be presented for the following variables:

- Adverse events and device-related adverse events in the clinical documentation.
- Effectiveness of the CapScan Device in collecting measurable quantities of metabolic breakdown products of sulfasalazine and for the identification of microbial enzyme genes.

All safety data will be summarized across the cohort with descriptive statistics. The incidence of adverse events during the treatment period will be summarized.

All adverse events will be classified by System Organ Class and preferred term according to the Medical Dictionary for Regulatory Activities (MedDRA). The latest version available at the time of coding will be used throughout the study.

All adverse events will be listed together with information on onset, duration, frequency, severity, seriousness, relationship to the investigational product, outcome and action taken. Frequency tables for severity and relationship to the Envivo Bio Device device will be provided by System Organ Class and preferred term.

The main analysis will not include events which started before the first use of CapScan Device number 1; only treatment emergent adverse events will be included in the summary tables.

VAS scores and changes from baseline will be presented by appropriate summary tables. Changes from baseline will be analyzed using Paired T-test or Signed rank test for two means (paired observations, or as appropriate).

Any deviation from the statistical analysis plan will be recorded together with an explanation of the deviation.

The data will be analyzed using standard statistical software (e.g., SAS [Cary, NC] or R [Vienna, Austria]).

12. SAMPLE SIZE CONSIDERATION

10 healthy subjects will be included in this study. The planned sample size was considered adequate by the Sponsor for this feasibility study. The study is not expected to show statistical significance or statistical power, but only to demonstrate safety and a trend for effectiveness and suitability of the sample collection process.

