9. STUDY ENDPOINTS

The study's endpoint is the regional measurement of sulfasalazine, the metabolic breakdown products of sulfasalazine in the digestive tract and peripheral circulation, and the gut microbiota in the digestive tracts of healthy volunteers.

Safety assessments will include the monitoring of subject-reported adverse events as communicated to the study staff.

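### Section 12 says the study will demonstrate safety, but up to 10 subjects and no safety criterion can only describe it; Section 11 gives proportions no interval and has no rule for Day 2 repeats

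*Combined protocol and SAP*

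**What the plan says.** **Aim and size.** Section 12 states that "The study is not expected to show statistical significance or statistical power". The rest of that sentence sets out what the sponsor does expect of it: "but only to demonstrate safety and a trend for effectiveness and suitability of the sample collection process". The section gives the size as 10, on the sponsor's judgement that this is adequate. The synopsis and Section 5 say up to 10. The synopsis describes a single-arm, open-label design.

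**Safety.** Section 9 and the synopsis rest safety on adverse events that subjects report. Section 11 adds that "All safety data will be summarized across the cohort with descriptive statistics" and that "only treatment emergent adverse events will be included in the summary tables". No section gives an acceptable event rate, a threshold or a safety hypothesis. Section 6.4 has every withdrawn subject replaced, whatever the reason.

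**Summary statistics.** Section 11 opens its plan for proportions with "For categorical variables, summary tables will be provided giving sample size, absolute" and goes on to relative frequency; no interval is listed. Intervals appear only for continuous variables: "percentiles and 95% CI (Confidence Interval) for means of variables".

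**Effectiveness.** The variable to be tabulated in Section 11 is "Effectiveness of the CapScan Device in collecting measurable quantities of metabolic breakdown products of sulfasalazine and for the identification of microbial enzyme genes". Section 9 says that the study's "endpoint is the regional measurement of sulfasalazine", its breakdown products and the gut microbiota. Neither section names a unit of analysis or a denominator.

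**Repeats.** The synopsis, Section 2.2 and Section 5 let the investigator request a repeat of the Day 2 procedures between Days 12 and 19 if the Day 2 devices were not retrieved or gave no usable samples. Usable is not defined. Section 11 does not mention repeats.

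**The concern.** Section 3 names safety and the efficiency of sample collection as the focus of the study. Both are exposed to the same gap between the claim and the analysis.

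For safety, the likely good outcome is few or no events. Section 12 would then let the report say that safety was demonstrated, while Section 11 would print a bare 0% with nothing beside it to show how little 10 subjects exclude.

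For collection, the same data can give different headline figures depending on whether the repeats count and whether the unit is the subject or the attempt. Section 2.1 describes a single-use device, so success at the first attempt is what bears on its performance. If the counting rule is chosen after the results are known, the choice can decide the headline.

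**Working it through.** **1. The plan's own figure.** The only figure is the size, 10 (up to 10 elsewhere). No alpha, power, event rate or precision target is given, so there is no calculation to reproduce.

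**2. What zero events would show.** The case of zero events is an illustration, not a figure from the documents. The exact (Clopper-Pearson) two-sided 95% upper limit for 0 of n is 1 − 0.025^(1/n):

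| Subjects | 95% interval for 0 events |
|---|---|
| 10 | 0 to 30.8% |
| 8 | 0 to 36.9% |
| 5 | 0 to 52.2% |

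Among the planned sizes, 10 is the best case. A one-sided 95% limit at n = 10 is 1 − 0.05^(1/10) = 25.9%, so the choice of interval does not change the message. For one event in 10 the two-sided interval is 0.3 to 44.5%.

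The chance of seeing no event in 10 subjects is (1 − risk)^10. For a true per-subject risk of 10% it is 0.90^10 = 0.349, and for 20% it is 0.80^10 = 0.107. A clean result is therefore quite compatible with a risk that would matter in healthy volunteers.

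**3. The same limit for collection.** If all 10 subjects gave a usable sample, the exact lower limit is 0.025^(1/10) = 69.2%.

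**4. Effect of the repeats.** Let A of n subjects succeed at the first attempt, m be repeated, and R of the subjects who failed first succeed on repeat.

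- Subject level, either attempt counts: (A + R)/n. As R cannot be negative, this equals or exceeds A/n.
- Pooled over attempts, when only first-attempt failures are repeated: (A + R)/(n + m). This rises or falls according to whether R/m is above or below A/n.

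With assumed data A = 7, n = 10, m = 3:

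| R | First attempt | Either attempt | All attempts |
|---|---|---|---|
| 0 | 7/10 = 70% | 7/10 = 70% | 7/13 = 53.8% |
| 2 | 7/10 = 70% | 9/10 = 90% | 9/13 = 69.2% |
| 3 | 7/10 = 70% | 10/10 = 100% | 10/13 = 76.9% |

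For R = 2 the exact intervals are 34.8 to 93.3% for 7/10 and 55.5 to 99.7% for 9/10. Section 11 permits any of the three columns.

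**5. Range over assumptions.** The expected either-attempt rate is p + (1 − p)·f·p·(1 − ρ), where p is first-attempt success, f the fraction of failures repeated and ρ the within-subject correlation. With f = 1 and ρ = 0, p of 60%, 70% or 80% becomes 84%, 91% or 96%. With p = 70%, f = 0.5 and ρ = 0.5 it is 0.70 + 0.30 × 0.5 × 0.70 × 0.5 = 75%. All these inputs are assumed; the documents give none.

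**The case against.** Section 12 itself disclaims significance and power and calls this a feasibility study; Section 11 calls the statistics mainly descriptive; safety is not in the objective in Section 4; and no decision rule hangs on the word demonstrate. This makes the safety point one of wording, but does not remove it: the sentence that gives up power keeps demonstrating safety as an aim.

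The synopsis promises individual listings of all measured variables, and Section 11 lists every adverse event. With so few subjects, a reader could probably separate first attempts from repeats and compute an interval. That helps transparency, but does not settle which figure is the headline.

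The Section 11 effectiveness variable could also be summarised as a continuous quantity, with the planned interval for means. That is possible, but collecting a measurable quantity reads at least as naturally as yes or no, and Section 3 speaks of collection efficiency.

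Four stronger readings are tempting and are not supported:

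- A reader might infer that counting repeats always inflates the result. That holds only for a subject-level, either-attempt count; a result pooled over attempts can move either way.
- A reader might infer that 10 is too few. The documents claim no power, and 10 is not in itself an error for a feasibility study.
- A reader might infer that a trend for effectiveness is out of reach. The documents leave it undefined; they do not show it to be unattainable.
- A reader might infer that the safety denominator is missing. It is partly indicated, by the reference to the cohort and the restriction to treatment-emergent events. What is unstated is whether replaced subjects stay in it.

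**Conclusion.** The point holds, and should be settled before results are seen. It is a mismatch between claim and analysis, not a fault in the design.

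A single-arm study of up to 10 subjects with no safety criterion can describe safety only: no events in 10 leaves risks up to 30.8% unexcluded, and fewer subjects leave more. Replacement could take the number exposed above 10, which would narrow this, so the precision belongs to the number actually exposed. Section 11 plans no interval for the proportions that carry the two focal questions.

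Section 11 also leaves open whether failure-triggered Day 2 repeats count. An either-attempt subject-level figure, which it permits, can only equal or exceed first-attempt performance; in the assumed example it turns 70% into 90%. The direction follows from the counting rule. The size rests on assumed data.

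**What to change.** 1. **Section 12.** Replace the aim of demonstrating safety and a trend for effectiveness with describing safety and estimating sample-collection feasibility. State the precision for the number of subjects actually exposed; for 10, zero events has an upper limit of 30.8% and 10 of 10 successes a lower limit of 69.2%.
2. **Section 11, safety.** Add exact (Clopper-Pearson) 95% intervals for the proportions of subjects with any treatment-emergent adverse event and with any device-related one, among all who swallowed at least one device, including those later replaced.
3. **Section 11, collection.** Make the first Day 2 attempt the main collection-success result, among all subjects who swallowed a Day 2 device, with an exact interval. Count non-retrieval as failure and define usable before samples are assayed. Give, per subject, how many Day 2 devices (0, 1 or 2) yielded a usable sample, because the repeat trigger can be read as one device lost or both. Report the Day 12–19 repeats separately.

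The cost is a more modest claim, possibly a lower headline success rate, and a few table columns. No subjects, procedures or clinical rules change.

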13. ETHICS

12.1 INSTITUTIONAL REVIEW BOARD

Prior to initiation of the study, the PI will submit the study protocol and significant amendments, sample Informed Consent Form (ICF), and any other documents that may be requested to the Instituional Review Board (IRB) for review and approval. The PI will request that the IRB provide written approval of the study and will keep on file records of approval of all documents pertaining to this study. The Investigator will not begin the study until the protocol and ICF have been approved by the IRB. The PI must agree to make any required progress reports to the IRB, as well as reports of device-related SAEs, life-threatening problems, or death. The PI will provide a copy of the written IRB approval of the protocol and ICF to the Sponsor prior to the start of the study.

12.2 ETHICAL CONDUCT OF THE STUDY

This trial will be conducted in compliance with this protocol, Sponsor instruction, the guidelines for good clinical practice (GCP), ISO 14155 parts 1 and 2 (2003), Medical Device Directive 93/42/EEC, Declaration of Helsinki; and applicable federal and local regulatory requirements.

All clinical work conducted under this protocol is subject to GCP rules. This includes an inspection by Envivo Bio Inc. or its designee, health authority, IRB representatives at any time. The PI must agree to the inspection of study-related records by health authority representatives and/or Envivo Bio Inc. or its designee.

12.3 SUBJECT INFORMATION AND CONSENT

At the Screening Visit the subject will be informed in detail about the investigational CapScan Device, and the nature of the clinical investigation with known or foreseeable benefits, risks and discomforts that subject may experience. The basic elements of informed consent as specified by ICH-GCP will be followed.

Written informed consent will be obtained from each subject to be involved in the clinical trial by using the Informed Consent Form (ICF) prior to the conduct of any study-related activity. Each subject will be given a copy of the written ICF. The subject must understand that throughout the study his or her participation remains voluntary and protected by the Declaration of Helsinki. The investigator is responsible for obtaining written (or witnessed) informed consent from potential subjects prior to study entry.

Subjects will be given time to read the informed consent and ask any questions before being asked to sign the form. The subjects will also be instructed that they are free to withdraw their consent and discontinue their participation in the study at any time without prejudice. If a participant withdraws during the Treatment Phase, the investigator will schedude an Early Termination visit.

Prior to the start of the study, the PI or PI designee will provide Envivo Bio Inc. with a blank copy of the ICF version approved by the IRB. Each subject's study file will include the signed ICF for study participation.

When the study Treatment Phase is completed and the CRF has been monitored, the ICF will be kept in the investigator's central study file for the required period of time.

12.4 SUBJECT INSURANCE

The sponsor has subscribed to an insurance policy covering, in its terms and provisions, its legal liability for injuries caused to participating persons and arising out of this research performed strictly in accordance with the scientific protocol as well as with applicable law and professional standards. The insurance was taken out with a maximum limit of \$1,000,000 per participating person.

Any impairment of health which might occur in consequence of trial participation must be notified to the insurance company. The study subject is responsible for notification. The insured person will agree to all appropriate measures intended to clarify the cause and the extent of damage as well as the reduction of damage.

During the conduct of the trial, the study subject must **not** undergo other clinical investigational treatment except for cases of emergency. The study subject is bound to inform the investigator immediately about any AE's and additionally drugs taken. The terms and conditions of the insurance should be delivered to the study subject.

12.5 INFORMING THE GENERAL PRACTITIONER

The PI should inform the study subject's regular physician of his/her participation in this study, by sending a letter to the physician, if the study subject agrees.

12.6 PERSONAL DATA PROTECTION

Envivo Bio Inc. complies with the principle of subject's right to protection against invasion of privacy. Throughout this trial, all data will be identified only by an identification number and subject initials. The data will be blinded in all data analyses. The study subject must be informed and consent is required that authorised personnel of Envivo Bio Inc. (Study Monitor, Auditor, Investors and Consultants etc.) and relevant Health regulatory agency will have direct access to personal medical data to assure a high quality standard of the study.

14. QUALITY CONTROL AND QUALITY ASSURANCE

Envivo Bio Inc. maintains quality assurance to ensure that clinical trials are conducted and data are generated, documented and reported in compliance with the protocol, GCP and applicable regulatory requirments.

This clinical trial may be audited by the Sponsor to determine whether the study is being conducted and monitored in compliance with the protocol as well as recognized GCP guidelines and local regulations. These audits will also increase the likelihood that the study data and all other study documentation can withstand a subsequent inspection by any regulatory authority.

Such audits, if necessary, will be pre-arranged with the site and conducted within a reasonable period.

The study may also be inspected by regulatory agencies. These inspections may take place at any time during or after the study and are based on the federal regulations, as well as ICH-GCP guidelines.

13.1 STUDY MONITORING

Monitoring of the study is the responsibility of the Sponsor. The study monitor will advise the PI regarding the practical conduct of the study and maintaining compliance with the protocol, GCP and all applicable regulatory requirements. Throughout the course of the study, the Sponsor and the study monitor will oversee the conduct and the progress of the study by frequent contacts with the investigator. This will include telephone calls and on-site visits. During the on-site visits, the CRFs will be reviewed for completeness with corresponding source documents. As part of the routine data monitoring, source documents will be made available for review by the study monitor. The study monitor will also perform subject's validation checks of the study particpant's questionnaires and may periodically request review of the Investigator's Study File to ensure completeness of documentation in all respects of clinical study conduct.

Upon completion of the study, the study monitor will arrange for a final review of the study files after which the files should be secured for the appropriate time period. The PI or PI designee will receive the study monitor during these on-site visits, cooperate in providing the documents for inspection, and respond to inquiries.

13.2 SOURCE DOCUMENT

The investigator(s)/Institution(s) will permit study-related monitoring, audits by or on behalf of the Sponsor, IRB review and regulatory inspections providing direct access to source data documents. Source documents are original records in which raw data are first recorded. These may be office / clinic / hospital records, charts, diaries, questionnaires and laboratory results, printouts, pharmacy records, care records, completed questionnaires for each study subject. Source documents should be kept in a secure and limited access area. All source documents must be accurate, clear, unambigous, permanent and capable of being audited. They should be made using a permanent form of recording (ink, typing, printing, optical disc etc). They should not be obscured by correcting fluid or have temporary attachements (such as removable self-stick notes). Source documents that are computer generated and stored electronically must be printed (for review by the study monitor), signed and dated by the investigator.

Source data for subjects should indicate date informed consent was signed, participation in clinical protocol number EB-01 and title, evidence that inclusion/exclusion criteria have been met and study execution dates.

